# **EFFECT OF PROSTAGLANDİN E1 TREATMENT ON PYLORİC WALL THİCKNESS İN NEWBORN PERİOD**

**DOCUMENT DATE: MAY 6, 2019**

## **Study Protocol:**

### **Effect of prostaglandin E1 treatment on pyloric wall thickness in newborn period**

Intravenous prostaglandin E1 infusion is referred to as ductus dependent diseases, in systemic (aortic blood flow) circulation (eg critical aortic coarctation, intermittent arcus aorta, hypoplastic left heart, transposition of great artery), or lung blood flow through patent ductus arteriosus ( For example, pulmonary valve atresia, tricuspid valve atresia, hypoplastic right heart) is a life-saving drug used to ensure that the duct remains open until a full, partial or temporary surgical correction or intervention is made. In the antenatal period, the placenta is a good source of prostaglandins. However, with the disappearance of the placental circulation after birth, many mechanisms ensure that the patent ductus arteriosus closes first functional and then anatomically. Due to these mechanisms occurring in the early days of life, babies who have ductus-dependent congenital heart diseases show themselves with severe clinical signs and symptoms such as cyanosis and circulatory disorders in this early neonatal period, when ductus begins to close when diagnosis and treatment are not performed. Echocardiography should be performed by the pediatric cardiology specialist as soon as possible after delivery to babies diagnosed in the antenatal period, and if a ductus-dependent congenital heart disease diagnosis is confirmed, PGE1 infusion should be started immediately, and the patient should be consulted with a pediatric cardiovascular surgery specialist and a surgical intervention plan should be provided as soon as possible. Due to these mechanisms occurring in the early days of life, babies who have ductus-dependent congenital heart diseases show themselves with severe clinical signs and symptoms such as cyanosis and circulatory disorders in this early neonatal period, when ductus begins to close when diagnosis and treatment are not performed. Echocardiography should be performed by the pediatric cardiology specialist as soon as possible after delivery to babies diagnosed in the antenatal period, and if a ductus-dependent congenital heart disease diagnosis is confirmed, PGE1 infusion should be started immediately, and the patient should be consulted with a pediatric cardiovascular surgery specialist and a surgical intervention plan should be provided as soon as possible. Prostaglandin E1 infusion is given as a continuous intravenous infusion. PGE1 has some side effects. The most common side effects are apnea, hyperthermia, and vasodilatation on the skin, they occur around 10-14% and are usually dose-related side effects. In addition, bradycardia, hypotension, convulsion, tachycardia, diarrhea, sepsis, necrotizing enterocolitis, hypernatremia, hyponatremia,

hypokalemia, respiratory depression, arrhythmia, congestive heart failure, gastric regurgitation, bleeding, anuria, hematuria and hypoglycaemia are more rare effects. The frequency and severity of these side effects usually depend on the dose of the drug and the time used. Many of these side effects disappear or decrease significantly when the medication is stopped or the dose is reduced. An important complication that can be seen with long-term use is cortical hyperostosis in long bones. Among the very rare side effects of the drug Prostaglandin E1 are hyperplasia of the gastric mucosa and the development of pyloric stenosis. Hypertrophic pyloric stenosis develops as a result of hypertrophy of circular pyloric muscles in the newborn period. Ultrasonography (USG) is the primary diagnosis and imaging method, because it does not contain radiation, it has replaced contrast studies. In ultrasonography, the thickness of the pyloric muscle from the mucosa to the serosa is more than 2-3 mm and the length of the pyloric canal is over 16 mm. In the literature, there is no study on the effect of PGE1 increasing the pyloric wall thickness in newborns, there is a case report from our hospital in this regard. In this study, we aimed to evaluate the effects of the drug on pyloric wall thickness prospectively with weekly ultrasonography measurements in infants given PGE1 infusion due to congenital heart disease. Ultrasonography measurements will be made at the bedside (with the ultrasonography device of our unit) by an experienced pediatric radiologist in pediatric cases. No intervention in the treatment, medical decisions and follow-up of patients will be made. Neonatal babies who were born in Hacettepe University Faculty of Medicine Ihsan Dogramaci Children's Hospital Neonatal Intensive Care Unit and who were receiving prostaglandin E1 infusion due to PDA-dependent congenital heart disease will be included in the study. Infants who do not have consent to participate, babies with chromosomal disease and hereditary metabolic disease will not be included in the study. In addition, babies who have an exitus in the first week of life and whose ultrasonography measurements cannot be obtained, and babies whose prostaglandin E1 infusion is discontinued by taking the second ultrasonographic measurement in the first week of life will be excluded from the study.

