### **Study Design:**

- Patients who have to receive Prostaglandin E1 treatment due to congenital heart disease followed in the neonatal department of our hospital will be included in the study after their consent and approval with their families without recording their identity information.

- Pyloric thicknesses will be measured by a pediatric radiologist once a week (at least twice) during the period when patients use PGE1.
- After reaching the sufficient number of cases (20 cases), increases in the pyloric wall thickness dimensions will be compared with statistical analysis. The number of cases was determined in accordance with the rate of hospitalization in our unit during the determined period (18 months). In this way, since the studies are in the form of a case report and the original article cannot be found in the literature, the observed power of the study will be calculated after the study is completed.

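### Does the unstated layer of pyloric thickness, with canal length unmeasured, let mucosal hyperplasia pass for hypertrophic pyloric stenosis?

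*Protocol*

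**What the plan says.** The title ("EFFECT OF PROSTAGLANDİN E1 TREATMENT ON PYLORİC WALL THİCKNESS İN NEWBORN PERİOD") and the aim in the narrative section ("we aimed to evaluate the effects of the drug on pyloric wall thickness prospectively with weekly ultrasonography measurements") both name the wall. Under *Study Design*, the measurement bullet is shorter and names no layer: "Pyloric thicknesses will be measured by a pediatric radiologist once a week", with at least two scans per infant. The bullet after it returns to wall thickness as the quantity whose increases will be compared.

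The muscle appears in two background sentences of the narrative section. One gives circular muscle hypertrophy as the cause of hypertrophic pyloric stenosis. The other gives its ultrasound appearance in terms of "the thickness of the pyloric muscle from the mucosa to the serosa is more than 2-3 mm and the length of the pyloric canal", with a limit of 16 mm for the latter. Just before these, the protocol lists two distinct rare effects of the drug: "Among the very rare side effects of the drug Prostaglandin E1 are hyperplasia of the gastric mucosa and the development of pyloric stenosis".

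No sentence says which layers the calipers span, and canal length is not among the planned measurements.

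**The concern.** The protocol names a mucosal effect and a muscular effect of the same drug, and its only anatomical description of a thickness is of the muscle. A measurement across the whole wall would add the two layers together. A rise could then come from mucosa alone and still be read as movement towards stenosis. Canal length, the second element of the background description, would not be there to help, and a limit written as a range cannot place an infant who measures between 2 and 3 mm.

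The stakes look high because this is the study's only outcome, it is a change between repeated scans, and a layer not captured at the bedside cannot be recovered afterwards. On that view, muscle thickness should be primary, mucosa and canal length secondary, and one cut-off fixed in advance.

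**Working it through.** The protocol gives no figure to reproduce here, so the check is mainly a comparison of text.

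**1. Which structure is named where**

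| Place in the protocol | Structure named | Role |
|---|---|---|
| Title | wall | outcome |
| Narrative section, gap in the literature | wall | rationale |
| Narrative section, aim | wall | outcome |
| *Study Design*, measurement bullet | none stated | procedure |
| *Study Design*, analysis bullet | wall | analysis |
| Narrative section, cause of stenosis | muscle | background |
| Narrative section, ultrasound appearance | muscle and canal length | background |

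The outcome does not move between structures. It is the wall wherever it is named as an outcome. The one bullet without a layer is followed directly by one that supplies the word.

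**2. Is stenosis an outcome?** The protocol sets no stenosis endpoint, count of cases or rule for classifying infants. Neither the 2-3 mm nor the 16 mm figure is applied to study infants. The protocol also states that treatment, medical decisions and follow-up will not be altered by the study.

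**3. The cut-off range.** Its relative width is (3 − 2)/3 = 33% of the upper value, or (3 − 2)/2 = 50% of the lower. The arithmetic is right, but the limit is never used, so no planned result depends on it.

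**4. Size of a mucosal contribution.** If the calipers include the mucosa,

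change in wall = change in muscle + change in mucosa.

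Let f be the share of the rise that is mucosal. Reading the whole rise as muscle then overstates the muscle effect by a factor 1/(1 − f):

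- f = 0: factor 1, no overstatement;
- f = 0.5: factor 2;
- f = 1: the rise is entirely mucosal and there is no muscle effect.

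The documents give no value for f, so these are illustrations over its full range. Two further conditions are needed: mucosa must lie inside the calipers, and the study must claim a muscle effect. The text states neither. The listed hyperplasia is gastric; that it thickens the measured pyloric wall is an inference.

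**5. What the missing landmark does to a change.** Suppose the convention includes an inner layer of constant thickness c. Then (later muscle + c) − (first muscle + c) = later muscle − first muscle, and c cancels. Including a layer that does not itself change therefore does no harm, provided the same convention is used at each of an infant's scans.

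**The case for a change.** The best case for a change is that the caliper convention belongs to data collection and cannot be left to an analysis plan. The only anatomical phrase, mucosa to serosa, does not say whether the mucosa is counted. If it is, a rise cannot be assigned to muscle; if it is not, wall is a loose name for muscle. A convention that drifted between scans would enter the within-infant change directly. Naming the landmarks would cost a sentence, and the extra caliper readings come from the same scan.

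Part of this stands. The layers are not stated, canal length is not planned, and a rise could not be firmly attributed to one layer or set against the full background description. But attribution to a layer is not the question asked. Wall thickness is a legitimate outcome for a first descriptive series, and it registers thickening of either layer. Making muscle primary would substitute another question, which is a trade-off rather than a correction. Drift is possible in principle, but the protocol assigns the scans to an experienced pediatric radiologist, and nothing in it suggests that the convention would vary. Canal length would be an optional extra that the aim does not need.

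**Conclusion.** No change is needed. The feared harm, mucosal hyperplasia counted as stenosis, requires an endpoint and a classification that the protocol does not contain. The complaint about the 2-3 mm range concerns a background figure that the study never applies. What survives is a gap in detail: the landmarks are unstated in the measurement bullet. The person holding the probe fills that gap sensibly, and the report can state the convention used.

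The effect on the planned result cannot be sized from the documents; the factor of two is a consequence of an assumed half share and nothing more.

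This conclusion assumes that the same convention is kept across each infant's scans, and that the report confines itself to wall thickness. If the authors went on to claim muscular hypertrophy or to count cases of stenosis, the missing layer and canal length would limit that claim, but the protocol plans neither.

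### Do the two descriptions of eligible infants, one by birth and one by follow-up in the unit, define different study populations?

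*Protocol*

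**What the plan says.** The opening section of the Protocol (Effect of prostaglandin E1 treatment on pyloric wall thickness in newborn period) gives the inclusion sentence. It begins "Neonatal babies who were born in Hacettepe University Faculty of Medicine", continues with the name of the children's hospital and its neonatal intensive care unit, and ends with those "who were receiving prostaglandin E1 infusion due to PDA-dependent congenital heart disease will be included in the study". The exclusions that follow are lack of consent, chromosomal disease, hereditary metabolic disease, death in the first week without measurements, and a last item covering infants whose "infusion is discontinued by taking the second ultrasonographic measurement in the first week of life will be excluded from the study". Birth in another hospital is not listed.

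Study Design, first bullet, describes the same infants as PGE1 patients "followed in the neonatal department of our hospital will be included in the study", with no condition on place of birth. The second bullet sets the scans: "once a week (at least twice) during the period when patients use PGE1". The third bullet gives the target of 20 cases and its basis: "The number of cases was determined in accordance with the rate of hospitalization in our unit during the determined period (18 months". The increases are to be compared once that number has been reached.

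**The concern.** Both sentences are written as operative inclusion rules, and nothing says which governs. Taken at their word they disagree about one kind of infant: born elsewhere, admitted to the unit, consented, on PGE1 for duct-dependent disease and scanned at least twice. That infant contributes an increase, so a literal reader would build two different data sets.

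In a study of 20 infants this could matter in three ways: how quickly cases accrue, whose increases are averaged, and to whom the result applies. There is also an argument that transferred infants differ in prior exposure. The background separates infants diagnosed antenatally, for whom "if a ductus-dependent congenital heart disease diagnosis is confirmed, PGE1 infusion should be started immediately", from those who present with symptoms as the duct closes, and it says of side effects that "The frequency and severity of these side effects usually depend on the dose of the drug and the time used". An infant treated before transfer may already have had days of PGE1 at the first scan.

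The last exclusion adds to the impression of loose eligibility. As printed, it appears to remove infants whose infusion ends with the second scan, although Study Design asks for two scans.

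**Working it through.** The protocol has no calculated figure that depends on the inclusion wording. The 20 is a feasibility count, with no significance level, effect size or standard deviation behind it. The check is therefore mainly a comparison of texts.

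**1. Is there a birthplace rule?** The opening sentence attaches *born* to an intensive care unit. Taken fully literally, it admits almost nobody. To obtain a rule restricted to infants born in the hospital, the reader must replace the printed unit with the hospital as a whole. Replacing *born* with *admitted* needs one word changed and leaves the unit as printed.

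**2. Which reading fits the rest of the document?**

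| Feature | Born in this hospital only | Admitted to this unit |
|---|---|---|
| Unit named in the opening sentence | does not fit | fits |
| Exclusion list silent on birth elsewhere | no conflict, but no support | fits |
| Study Design: followed in the department | adds an unstated limit | fits |
| 20 cases taken from the unit's admissions | needs a different count | fits |

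Each row fits the admission reading, and none favours the birth reading.

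**3. What if the birth rule were meant?** The planned rate is 20/18 = 1.11 cases per month. Let *s* be the share of infants born elsewhere. The protocol does not give it, so 10, 25 and 50% are assumed, together with the assumption that the admission count includes these infants.

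- Cases in 18 months = 20(1 − *s*): 18, 15, 10.
- Months to reach 20 = 18/(1 − *s*): 20, 24, 36.

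Since the comparison is made after 20 cases have been reached, the second line is the relevant one. The number analysed stays at 20 and the calendar moves.

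**4. Effect on the mean increase.** If mean increases differ by *d* between the two groups, including or omitting infants born elsewhere moves the overall mean by *s* × *d*. With *d* = 0.5 SD, also assumed, this is 0.05, 0.125 and 0.25 SD. For scale, the 95% half-width for a mean of 20 increases is t(0.975; 19)/√20 = 2.093/4.472 = 0.47 SD. If *s* = 0 or *d* = 0, the mean does not move.

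**5. The last exclusion.** The likely intent is that the infusion stopped before the second scan, which agrees with the minimum of two scans. On that intent, the only infants left unnamed have a single scan and stop after the first week. They have no increase and cannot enter the comparison. Even as printed, the clause reaches very few infants, because weekly scans leave hardly any room for a second one in the first week of life.

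**The case for a change.** The strongest case for acting is that eligibility belongs in the protocol, that it is stated twice in different terms, and that the document never says *born* is a slip. With 20 infants, a handful of eligibility decisions can be visible in the result, and correcting the wording costs almost nothing. The textual part of this stands: the sentences do differ, and a single word would align them.

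The argument about consequences is weaker. The background does not link antenatal diagnosis to birth in this hospital, or late presentation to birth elsewhere. The sentence on duration of use refers to the side effects listed before it; pyloric stenosis is introduced only afterwards. Prior exposure at the first scan is also not peculiar to transferred infants, since Study Design places the scans within the infusion period and does not tie the first one to its start. The share born elsewhere and any difference in means are both outside the document.

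One point remains open. If recruitment were closed at 18 months whatever the count, a strict birth rule would reduce the number analysed and not only delay it. But the protocol makes the comparison conditional on reaching 20, so that is not what it describes.

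**Conclusion.** The difference in wording is real but clerical. The natural reading, infants admitted to the unit and receiving PGE1 there, makes the two sentences agree and is the only one that matches the unit named and the basis of the 20 cases. An investigator screening infants in that unit would be expected to apply it without being told.

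Nothing in the design or analysis depends on the choice in a way that would alter the plan. Each increase is a within-infant difference and is soundly estimated wherever the infant was born; birthplace affects only the description of the population. No stated number is shown to be wrong. The possible effects, 2 to 18 additional months of recruitment or a shift of 0.05 to 0.25 SD in the mean, arise only if the birth rule was truly intended and the assumed shares and difference hold. Recording and reporting results by place of birth would add little: on the same shares the smaller group would hold 2 to 10 of 20 infants. The last exclusion is likewise a matter of wording, and no infant with a usable increase is lost on its likely intent. Both phrases can be tidied if the document is reissued; neither warrants a change to the plan.

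### Does the exclusion tied to the first week of life conflict with the rule of at least two weekly scans during PGE1?

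*Protocol*

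**What the plan says.** The narrative part of the protocol gives the aim as evaluating pyloric wall thickness "prospectively with weekly ultrasonography measurements in infants given PGE1 infusion due to congenital heart disease". It ends with two exclusions that refer to age. One covers "babies who have an exitus in the first week of life and whose ultrasonography measurements cannot be obtained". The other covers "babies whose prostaglandin E1 infusion is discontinued by taking the second ultrasonographic measurement in the first week of life".

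The second bullet of Study Design sets the measurement schedule: a paediatric radiologist measures thickness "once a week (at least twice) during the period when patients use PGE1". The third bullet gives the comparison: "After reaching the sufficient number of cases (20 cases), increases in the pyloric wall thickness dimensions will be compared with statistical analysis". The figure of 20 comes from the unit's admission rate over 18 months, not from a power calculation. The protocol does not fix the day of the first scan or say whether the 20 are enrolled infants or infants with two scans.

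**The concern.** Both rules bear on which infants contribute an increase, and they run on different clocks. The exclusion wording allows two readings, and each seems to leave a fault.

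- **Literal reading:** the second scan falls in the first week of life. Weekly scanning makes that nearly impossible. Where it does happen, an infant with the required two scans would be excluded.
- **Probable meaning:** the infusion ended in the first week of life before a second scan. An infant first scanned at 3 days whose infusion ends at 9 days then has one scan on a strict 7-day schedule, yet the exclusion does not name this infant.

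Starts after the day of birth are plausible. The background says that undiagnosed, untreated infants "show themselves with severe clinical signs and symptoms such as cyanosis and circulatory disorders in this early neonatal period". If one-scan infants were counted among the 20, fewer than 20 would supply an increase, and two people applying the text might assemble different case sets.

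**Working it through.** The protocol has no figure to reproduce here: it states no alpha, power, effect size or standard deviation. The check is a day count, followed by a comparison of the two rules.

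**Inputs.** From the protocol: weekly scans, a minimum of two during PGE1, 20 cases. Assumed: birth is day 0, the first scan is at PGE1 start at age s days, scans are 7 days apart, PGE1 stops at age t, and the first week of life ends on day W, with W = 6 or 7.

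**Literal reading.** The second scan is at s + 7, and it lies in the first week only if s + 7 ≤ W.
- W = 6: s ≤ −1, so never.
- W = 7: s ≤ 0, so only with a first scan on the day of birth.
- With 6-day spacing: s ≤ 0 (W = 6) or s ≤ 1 (W = 7). With 5-day spacing: s ≤ 1 or s ≤ 2.

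On the stated schedule the exclusion therefore describes almost nobody. At an assumed growth of 0.08 mm/week, a second scan squeezed into the first week would show at most 0.08 × (7 − s)/7, which is 0.069, 0.046 or 0.023 mm for s = 1, 3 or 5, against 0.080 mm over a full week. Infants caught by the criterion are excluded, so their short-interval increases never enter the comparison.

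**Probable meaning.** An infant has one scan and is not named by the exclusion if W < t < s + 7. With W = 7:
- s = 1: no such day.
- s = 3: t = 8 or 9.
- s = 5: t = 8 to 11.

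The gap in the exclusion wording is real on a strict 7-day grid. Its size cannot be taken from the protocol. For infusion length L, the expected number of one-scan infants among 20 not excluded is 20 × g / (P(L ≥ 7) + g), where g = P(7 − s < L < 7). For example, take an exponential L with mean 14 days and s = 3:
- g = e^(−4/14) − e^(−7/14) = 0.751 − 0.607 = 0.145
- 20 × 0.145 / (0.607 + 0.145) = 3.9

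With s spread evenly over 0 to 5 days, exponential and gamma (shape 2) lengths give 6.4 to 7.3, 2.8 to 3.4 and 1.5 to 2.3 infants for mean lengths of 7, 14 and 21 days. With s limited to 0 or 1, the count is about 0.4 to 1.9 across those lengths. With s = 0 it is 0.

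**Setting the rules side by side.** Take the infant with s = 3 and t = 9.
- Exclusion sentence: silent.
- Study Design, second bullet: two scans during PGE1 are required, and this infant has one.
- Study Design, third bullet: increases are compared, and one measurement gives none.

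The infant cannot enter the comparison whether or not the exclusion names the case. Moreover, the protocol says weekly, not every 7 days. If one scan is taken in each week of life, this infant is due a second scan from day 7 onward and can have it before stopping on day 9. On that schedule, for infants first scanned in week one, stopping in week one means one scan and continuing into week two allows a second, so the two rules largely coincide.

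**Power.** For a paired t-test at two-sided 5% and 80% power, the detectable change is 0.66 SD with 20 infants, 0.72 SD with 17 and 0.85 SD with 13. The last two apply only if the 20 are enrolled infants and 3 or 7 of them lack a second scan. If the 20 are infants with two scans, nothing changes.

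**The case for a change.** The strongest case for a change is that this is eligibility text, which belongs in the protocol and cannot be left to an analysis plan. The two-scan minimum is written as a measurement schedule, not as an exclusion or a rule for counting cases. Even the charitable reading leaves one-scan infants unnamed, and one sentence would settle it with no extra scans.

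Part of this stands. The exclusion is garbled, it does not match the minimum at every start and stop age, and the protocol does not say whether a one-scan infant counts toward the 20. A literal reader could also drop an infant scanned twice in week one, but only if the scans were closer together than weekly or began on the day of birth.

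The consequence does not stand. Disagreement over the analysed set requires a reader to keep as a case an infant who fails the stated minimum and has no outcome. The argument for late starts is also weaker than it looks: the symptomatic presentation in the background concerns infants without diagnosis and treatment, whereas for antenatal diagnoses the same text calls for prompt echocardiography and immediate PGE1 once the diagnosis is confirmed. The inclusion sentence describes babies born in the hospital. Very early first scans, where the gap is small or absent, are at least as well supported as an even spread over days 0 to 5.

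**Conclusion.** No change to the plan follows. The exclusion is clumsily worded on an age clock, most likely through translation, and Study Design supplies the rule that matters: at least two scans during PGE1, with increases as the quantity compared. Replacing the exclusion with one for fewer than two scans would mostly restate that minimum. Recording scan intervals and infusion duration is detail that an analysis plan may hold.

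No effect on the comparison has been shown. The one-scan counts depend on assumed start ages, assumed infusion lengths and an exact 7-day grid. The larger detectable effects depend on counting enrolled infants as the 20, and the protocol sets no power target. Under any sensible reading the results describe infants treated long enough for two scans. Stating how many infants had only one scan is ordinary reporting and needs no amendment.

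This conclusion assumes that the two-scan minimum is applied as written and that one-scan infants are not counted among the 20 cases.
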